4.3 Does NEYAI have an impact?

We propose a quasi-experimental design⁴⁷ since, in the circumstances, this is the most appropriate way of answering the first evaluation question: does NEYAI have an impact on children and their parents by comparison with a matched sample of those who have not participated in NEYAI? This design involves comparing the treatment group (those who receive the 'NEYAI treatment') with a comparison group (those who receive the 'usual treatment'), both groups matched in terms of demographic and socio-economic characteristics. More specifically, this design involves three related elements:

- (i) assessing the treatment group at baseline (before the NEYAI intervention) and at follow-up (immediately after the NEYAI intervention) in order to measure any changes in the intervening period;
- (ii) assessing a matched comparison group at baseline (without any intervention other than 'treatment as usual') and at follow-up (using the same intervention period as the treatment group) in order to measure any changes in the intervening period;
- (iii) comparing changes in the treatment group and the comparison group in order to establish the difference in outcomes between NEYAI intervention and 'treatment as usual', thereby measuring the *net* impact of the intervention.

The measurement of difference in outcomes between the treatment and comparison groups - 'between-group differences' - is an acceptable and accepted way of measuring impact provided that all of the measured differences between the two groups are taken into account. However it also needs to be recognised that it is not a perfect comparison since, due to the absence of randomisation⁴⁸, there may be unmeasured differences between the two groups which could account for any difference in the observed net impact. The perfect comparison involves an experimental design, usually called a randomised control trial (RCT), but this is not an option since the NEYAI was not designed with that in mind and, moreover, could be difficult to design in practice. Nevertheless, the quasi-experimental method provides an important degree of confidence that,

47 A quasi-experimental method involves setting up two groups (an treatment and comparison group) except that the process of random allocation is not used to establish each group, either because of ethical or practical considerations, or both. In the case of NEYAI, the reasons are entirely practical due to the design of the programme which effectively rules out the possibility of random allocation. The absence of random allocation means that it is not possible to be sure that the treatment and comparison groups are perfectly matched. Nevertheless, when both groups are matched on a range of measured variables – bearing in mind that, due to the absence of random allocation, there is no control over unmeasured variables - it may be reasonable to infer that differences between the treatment and comparison groups are attributable to the programme. In this way, the quasi-experimental method is sometimes regarded as an appropriate test of a programme, even if second best to a randomised control trial. Where a comparison group is not possible, the use of advanced statistical techniques to control for the separate influence of each variable in the dataset is a useful alternative except that it cannot control for the influence of participating in a programme versus not participating.

48 The effect of randomisation is to ensure that both groups are matched on measured as well as unmeasured characteristics.

where net impacts are detected, they are more likely to have occurred as a result of NEYAI rather than by chance.

4.4 How does NEYAI have an impact?

Turning to the second question in the evaluation - if NEYAI has an impact, how does this come about, for whom, in which projects, using what type of intervention(s), etc? – the research design involves using structural equation modelling (SEM)⁴⁹ to identify all the possible sources of statistically-significant variation in outcomes between the treatment and comparison groups. This approach is based on confirmatory programme evaluation and involves testing each hypothesis in the ‘logic model’ against the evidence. The detailed steps involved in this analysis are detailed below (Section 9). It is noteworthy that many of the pathways postulated in the logic model above (Figure 1) have themselves been identified through previous confirmatory studies of early years interventions, while SEM was also used to identify the pathways in Figure 2 above.

SEM falls into the broad realm of multiple-regression analysis but, unlike ordinary regression analysis, it allows different levels of influence to be investigated⁵⁰. By comparison with ordinary regression analysis, it also deals in a more satisfactory manner with the distinction between the ‘measurement model’ which estimates each latent variable and associated degree of error (such as the left-hand side of Figure 2) and the ‘structural model’ which describes associations between those latent variables (such as the right-hand side of Figure 2).

Statistical analysis, however sophisticated, cannot interpret results much less infer that a statistically-significant association between variables implies that they are causally related. That is why the interpretation of results is a key part of the research design. Establishing a causal link between inputs, pathways and outcomes is fundamentally a matter of interpretation and requires that verifiable criteria are met, to some degree at least, in order to have confidence in the validity of

49 All modelling will use EQS 6.1 Structural Equation Modelling Software (Bentler, 1995).

50 Traditionally, it has been common for researchers, using regression analysis, to treat all variability in an outcome as attributable to individual-level variation (level 1), and to assume that each individual-level observation is independent and not influenced by the setting which individuals may share such as the same neighbourhood, school, hospital, programme, etc (level 2). The effect of this is to over-estimate individual-level influences, where they occur, and to overlook group-level influences which are properly attributable to setting. When these two sources of variability are not separated in statistical analysis, and only sources of variation at level 1 are considered, there is a danger that the influence of predictor variables may be over-estimated since sources of variation at level 2, where they occur, are assumed to occur at level 1 only; correspondingly, there is an under-estimation of the variability that is random or unexplained, usually referred to as ‘the error variance’. Multi-level modelling was invented to overcome these problems which are not just ‘statistical’ problems but have practical consequences. The practical consequence of this is that, when drawing out practice or policy implications of analysis, one may place too much importance on individual-level predictors or, conversely too little on how these individual-level predictors may vary in their influence from one setting to another.

the interpretation. Within confirmatory programme evaluation⁵¹, and in other fields of inquiry where causal inference is required such as epidemiology⁵², these criteria typically include the following:

1. Temporality

This is generally regarded as the most basic criterion of causal inference since a cause must precede its effect in time. That is why the research design for this evaluation is based upon a 'before-and after' comparison of those who participate in NEYAI with those who do not.

2. Size & Strength

This criterion suggests that, other things being equal, the larger the association between programme participation and outcome, the more likely the association represents a true effect. The requirement of 'other things being equal' draws attention to the possibility that the association may be due to the confounding effects of selection bias; for example, those who participate in the programme may be different from those who do not. Within the limitations of quasi-experimental design, these confounding effects are taken into account by controlling for all of the measured characteristics of programme participants.

3. Gradient (dosage-response)

This criterion implies that a causal inference is more justified if, other things being equal, there is a direct relationship between programme participation (such as the number of days or sessions attended, number of contact hours, number of years of participation) and the outcome. This criterion will be difficult to apply in this evaluation, particularly at initiative-level, because each project has a unique programme intervention with the result that dosages are not in equivalent units across projects. Moreover, within some projects, the concept of dosage is not clearly defined. Although gradient effects have been established in a number of early childhood evaluations⁵³, the dosage-response relationship may be direct inverse⁵⁴.

4. Specificity

This criterion refers to an association between a programme and an outcome which is quite specific to the theory underpinning the programme. For example, if NEYAI projects which focus on language or numeracy development have greater impact on cognitive outcomes than on social skills this would suggest, other things being equal, a causal link between those interventions and outcomes. Similarly, NEYAI projects which focus on enhancing the capacity of parents and which have a

51 See, for example, Reynolds, 2005.

52 See, for example, Bradford Hill, 1965.

53 Examples include studies of the Abecedarian Project (Campbell and Ramey, 1995), the Chicago Child-Parent Centers (Reynolds, 1994; Reynolds and Temple, 1998), and the Infant Health and Development Program (Ramey, et al., 1992).

54 As indicated above, the NICHD Study of Early Child Care and Youth Development found that higher quality childcare was related to better cognitive, language, and pre-academic outcomes but behaviour problems tended to increase for children who spent more time in childcare (NICHD Early Child Care Research Network, 2006a; 2006b). Similarly, the evaluation of Sure Start suggested that, 'within ... deprived communities, children from relatively more disadvantaged families (that is, teen mothers, lone parents, workless households) appeared to have been adversely affected by living in an SSLP community' (Belsky and Melhuish, 2007:49).

greater impact in that area compared to other projects would strengthen the causal inference about the efficacy of their intervention.

5. Consistency

Consistency refers to an association between a programme and a set of outcomes which has been found consistently across sample populations, at different times and places, under different types of analyses and model specifications, and for similar programme theories. The more consistent the results, the more robust are the causal inferences. Consistency can be 'within-study' which is where the same result is produced using different analytic techniques, or 'between-study' where the result is consistent with findings from previous studies using different samples, social contexts, and programme variations.

6. Coherence

Coherence is essentially about whether the interpretation offered provides a convincing story about the effects of the programme. This criterion focuses on plausibility of the causal mechanisms (or 'active ingredients') which are proposed to explain the association and builds on existing knowledge as well as the theory underpinning the programme. In this evaluation, the coherence criterion will be addressed by building a statistical model of pathways leading to outcomes and then supplementing this by case studies of how those pathways may operate in practice. This aspect of evaluation is often overlooked since, as Reynolds has observed, 'relatively little attention in the evaluation field has been devoted to the pathways or causal mechanisms of change, or more broadly, the environmental conditions that help maintain or enhance effectiveness.'⁵⁵

These criteria are designed to improve the validity of causal inferences while also recognising that knowledge, in the scientific context, always contains elements of conjecture and the possibility of refutation – hence the characterisation of science in a once famous work as 'conjectures and refutations'⁵⁶. In this evaluation, the focus of interpretation will be on projects where a net impact has already been established and where the collection of additional qualitative data may help explain how that net impact came about, particularly where this is not apparent from the statistically-significant associations between inputs, pathways and outcomes. This analysis, in turn, is designed to provide a reasonable platform for drawing conclusions and making recommendations about the type of actions that may be required at the level of practice and policy to improve the quality of care and education for children in their early years.

⁵⁵ See, for example, Reynolds, 2005:2406.

⁵⁶ Popper, 1963.

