Returning to the logic model, the precise way in which the different elements of the model operate in practice, and connect with each other as covariates or causes, cannot be represented in advance of the evaluation. However as a simple framework, it serves to clarify the type of research design which is needed to meet the objectives of the evaluation. It does this by describing the theory behind the programme and identifying the different categories of data that need to be collected in order to test if the programme is achieving its expected outcomes and, if so, how. In other words, the logic model sets out a set of hypotheses which will be tested through a statistical model of how NEYAI actually works, based on the evidence available.

4. Research Design

The overall objective of NEYAI can be stated in relatively simple terms: to improve the capacity of childcare services in order to improve outcomes for children and their parents. Equally, the questions at the heart of this evaluation can also be stated in relatively simple terms:

- (i) Does NEYAI have an impact on children and their parents by comparison with a 'matched' sample of those who have not participated in NEYAI?
- (ii) If NEYAI has an impact, how does this come about, for whom, in which projects, using what type of intervention(s), etc?

Designing a research project in order to answer these questions with robust scientific evidence is not a simple undertaking however. That is why it may be useful to begin by setting out some of the challenges encountered in preparing this research design.

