The first consideration is the minimum sample size required to ensure that statistical tests are able to detect a difference between the treatment group and the comparison group. This is called the power of a statistical test and the convention is that a sample which allows differences to be detected in 80% of cases (referred to as a power of 0.8) is acceptable. Conversely, this convention accepts the likelihood that differences between the treatment and comparison group may not be detected in 20% of cases.

The second consideration is the level of significance attached to any result produced by a statistical test. The convention here is that results should be true in 95% of cases (referred to as $p=0.05$). Conversely, this convention accepts that differences detected between the treatment and comparison groups may not be true in 5% of cases.

The third consideration is the effect size which is expected as a result of the programme. As explained in the previous section, the impact of a programme is typically expressed in terms of effect sizes and most effective programmes for children and families tend to achieve effect sizes in the range 0.2 to 0.5 across a wide range of outcome domains and this seems to be an appropriate target for the NEYAI (see Appendix One). Based on these considerations, a sample of 35 participants is appropriate for each group, bearing in mind that most of the statistical analysis will be based on the combined samples of treatment group (385 cases) plus comparison group (385 cases), equal to 770 cases. This is a safe sample size by comparison with more celebrated evaluations of early years programmes⁷¹.

70 Request for Tender For Evaluation of National Early Years Access Initiative, 2011:8.

71 One of the more celebrated evaluations of a pre-school programme - High Scope which was first introduced into Perry Elementary School in the Michigan city of Ypsilanti in 1960 and has tracked children from then till age 40 – is based on a combined sample of 123 (58 in the treatment group and 65 in the control group) (Schweinhart, Montie, Xiang, Barnett, Belfield and Nores, 2005). Similarly, the Carolina Abecedarian

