9.1.2 Construction of multivariate outcome measures. The outcomes of the initiative, as shown in the logic model in Figure 1, are improved child and parent outcomes. The logic model also shows intermediate outcomes, notably improved staff capacity, which may act as a pathway to final outcomes. These outcomes are latent variables in the sense that each of them is based on an underlying construct which is manifested through various ‘proxies’ or ‘indicators’. This is illustrated in Figure 2 above and shows how child and parent well-being are latent variables which manifest through, and are measured by, a range of indicators; that is why the arrows point from the latent variable to the indicators which measure it. Detailed analysis will be undertaken to construct robust latent variables for all outcome measures and establish their validity (both discriminant and convergent). There are many precedents for measuring child and parent outcomes in this way but the measurement of staff capacity, particularly in the childcare sector, is more novel and will require a more exploratory approach. This part of the analysis, which establishes the ‘measurement models’ for the evaluation, is a crucial building block for the subsequent analysis, and is effectively a test of the conceptual framework underpinning each of the questionnaires as illustrated in Figures 3, 4 and 5 above.

9.1.3 Construct a model of child and parent well-being. This will build on the ‘measurement model’ just described and analyse how the latent variables relate to each other. The resulting ‘structural model’ will combine the measurements of child and parent well-being with all possible influences within the dataset to produce an overall model, somewhat similar to the model described in Figure 2 above. The analysis will distinguish between an ‘optimal’ model, which utilises the NEYAI dataset only, and a ‘comparison’ model based on those concepts shared between NEYAI and GUI. The rationale for this is that GUI has less data on parental well-being compared to NEYAI and this may influence the resulting models of child and parent well-being. The results of this analysis will allow us to compare key outcome measures between the two datasets and thus allow us to position the NEYAI sample relative to the national GUI sample.

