9.2 Follow-up Data Analysis

The follow-up data analysis will involve the following components.

9.2.1 Repeat the analysis described in paragraphs 9.1.2, 9.1.3 and 9.1.4 above. This is necessary in order to make sure that, when baseline and follow-up data are merged, the latent variables underpinning the measurement and structural models are based on identical structure matrices and measurement scales. That is the only way of making valid comparisons between baseline and follow-up when using multi-dimensional outcome measures. This step will involve a recalibration of all latent concepts using the combined dataset since, only when these conditions are satisfied, will we be able to present robust ‘before-and-after’ comparisons of outcomes. The adjusted models of child, parent and staff outcomes will be presented graphically along with an interpretation of their meaning and implications.

9.2.2 Having established consistent and robust measurements for all multi-dimensional outcomes relating to children, parents and staff, we will present results on impact by comparing the difference between baseline and follow-up scores. Improvements in outcomes will be expressed in terms of a comparison of means, standard deviations and effect sizes. As explained earlier, the use of effect sizes is a simple way of standardising and comparing two sets of scores and allows the impact of NEYAI to be measured in a way that is comparable to other early years programmes. Table 3 is a draft of the format that will be used to present this data.

Table 3 Format for Presenting Effect Size Scores in the Final Report

Vari- able	Effect Size Score for Treatment Group (TG)												Effect Size Score for Comparison Group (CG)										
	BC	CC	CK	CN	DD	DL	FL	LD	LK	RO	TT	All	1	2	3	4	5	6	7	9	10	All	
*																							
**																							

*Denotes a statistically significant difference between treatment group and comparison group for that variable.

**Denotes a statistically significant difference between treatment group or comparison group and the GUI for that variable.

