9.2.3 Examine possible pathways associated with each net impact. Using Structural Equation Modelling, analysis of the combined dataset of treatment and comparison group will estimate if there is a difference in outcomes between the two groups and whether, in turn, this is related to the interventions in any or all of the projects. Only when this has been established, will the analysis examine the association between these interventions and other independent variables, since that is how the pathways suggested in the logic model are tested against the evidence. This will involve taking one outcome measure each for children, parents and staff, and then developing a statistical model to explain the pathways by which that improved outcome came about. We will also build a statistical model which combines all three outcome measures in order to show how the well-being of children, parents and staff are inter-connected. Within these models, relationships between variables are measured by standardised regression coefficients and each coefficient measures the unique influence of each variable on the outcome, controlling for all other variables which affect that outcome. This method of analysis is capable of yielding statistically robust insights into the pathways by which change occurs in outcome variables and is increasingly regarded by researchers and statisticians as the appropriate form of analysis for this type of evaluation.

9.2.4 Describe in more detail the interventions and pathways associated with positive impacts, as identified in the models. This is important because it is unlikely that the statistical models, on their own, will contain an exhaustive account of all factors associated with statistically-significant improvements in outcomes. That is why data on the intervention delivered by each project is important (see Section 6.4 above) as well as data from evaluation of the learning community (see Section 6.7 above). Additional case-study data, collected from projects identified as having a positive impact, may also cast light on questions which cannot be addressed easily or

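### The pathway analysis is labelled confirmatory but, as described, is largely an open search, so its significant paths cannot all be read as tested mechanisms

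*Protocol*

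**What the plan says.** Section 4.2 adopts confirmatory programme evaluation: state the programme theory first, then test the hypothesised mechanisms where a main effect has been found. Footnote 46 ties that approach to a model fixed beforehand. Section 4.4 applies it to core question (ii), saying that each logic-model hypothesis will be tested, and refers the reader to Section 9 for the detailed steps.

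The procedure is described differently:

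- Section 4.4 uses structural equation modelling "to identify all the possible sources of statistically-significant variation in outcomes between the treatment and comparison groups".
- Section 3 says that the precise way in which the elements of the logic model operate and "connect with each other as covariates or causes, cannot be represented in advance of the evaluation".
- Section 9.1.3 combines child and parent well-being "with all possible influences within the dataset to produce an overall model".
- Section 9.2.1 repeats 9.1.2 to 9.1.4 at follow-up. It adds: "This step will involve a recalibration of all latent concepts using the combined dataset".
- Section 9.2.3 takes one outcome each for children, parents and staff, and then develops a model to explain how the improvement came about. It says: "This method of analysis is capable of yielding statistically robust insights into the pathways by which change occurs in outcome variables".

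The only exploratory element acknowledged in the analysis is the measurement of staff capacity (9.1.2).

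**The concern.** A confirmatory test needs its hypotheses fixed before the data that judge them are examined. A procedure that looks for every significant source of variation, over influences limited only by the dataset, and shapes the model after the outcome is known, generates hypotheses. Both are legitimate, but a significant path means something different in each. In the first it is a result with a known error rate. In the second it is a lead.

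The significant paths are the statistical answer to core question (ii): how any impact came about and for whom. They guide the more detailed description of interventions in 9.2.4 and the implications for action in 9.2.6. If searched paths carry the confirmatory label, chance findings could be passed to practice and policy as tested mechanisms.

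**Working it through.** **The protocol's own figures.** The protocol gives no number of pathway tests and no expected number of false paths. Its only error rates are in Section 5, for group comparisons. On significance it accepts that "differences detected between the treatment and comparison groups may not be true in 5% of cases". On power it says that "a sample which allows differences to be detected in 80% of cases (referred to as a power of 0.8) is acceptable". It expects effective programmes to "tend to achieve effect sizes in the range 0.2 to 0.5", with 385 per group (770 in all).

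Taking a two-sided 5% level (sidedness is not stated), a standardised effect of 0.2 and no clustering or attrition:

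- n per group = 2 × (1.960 + 0.842)² / 0.2² = 393, against 385 stated.
- Power at 385 = Φ(0.2 × √(385/2) − 1.960) = Φ(0.815) = 0.792, against 0.80.

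The stated size is therefore reproduced for one simple comparison of two groups. It says nothing about a search over many paths.

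**False paths within one model.** Let K be the number of candidate paths that are truly null. K is an assumption. The 5% level per path is also an assumption, carried over from Section 5, because no threshold for paths is given. For independent tests:

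- expected false paths = 0.05 × K
- chance of at least one = 1 − 0.95^K

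| K | Expected | At least one | Two or more |
|---|---|---|---|
| 10 | 0.5 | 0.40 | 0.09 |
| 20 | 1.0 | 0.64 | 0.26 |
| 40 | 2.0 | 0.87 | 0.60 |
| 60 | 3.0 | 0.95 | 0.81 |

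**Sensitivity to correlation.** Section 9.2.3 describes coefficients that control for all other variables. Multiple regression stands in for that here: 770 cases, a null outcome, and predictors with mutual correlation 0 or 0.5, 500 data sets per setting.

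- K = 20: mean 0.99 and 0.99 significant paths; at least one in 63% and 62% of data sets.
- K = 40: mean 2.13 and 2.04; at least one in 89% and 86%.

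If instead the test statistics themselves had pairwise correlation 0.5, the expected counts would stay at 1 and 2, but the chance of at least one would fall to 0.42 (K = 20) and 0.57 (K = 40).

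**Refitting on the same data.** With 770 cases and independent predictors, keeping the paths with p < 0.05 and refitting on the same data leaves on average 0.87 (K = 20) and 1.67 (K = 40) false paths. Refitting removes few of them.

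**The gate.** Section 9.2.3 looks at pathways only once a group difference has been shown, in any or all of the projects. Section 4.5 assesses 11 projects on three sets of outcomes, which is 11 × 3 = 33 assessments. With no true effect and independent tests at 5%:

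- three pooled tests: 1 − 0.95³ = 0.14 chance that at least one passes
- 33 project-level tests: 1 − 0.95³³ = 0.82

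How strict the gate is depends on how it is opened. When it opens on a true effect, the table above still applies to the paths examined afterwards.

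**The case against.** The case for the protocol is substantial.

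- **There is a priori content.** Section 3 names three pathways and calls the logic model a set of hypotheses to be tested. Only the precise connections are left open. This stands, and it makes the remedy easy. It does not cover the wider search.
- **The open-ended wording in 9.1.3 concerns the baseline well-being model**, not the impact pathways. True, but 9.2.1 repeats that model at follow-up, and 4.4 has its own open-ended wording for the pathway analysis.
- **The recalibration in 9.2.1 has a sound purpose**: the same scales at both waves. A reader might infer that recalibration itself creates false pathways. The documents do not support that. The difficulty lies in the repeated structural models and the pathway model built afterwards.
- **There are safeguards.** The gate limits when pathways are examined. Section 4.4 says that significance does not establish cause and lists temporality, strength, gradient, specificity, consistency and coherence. Section 9.2.6 warns against over-interpretation. These temper interpretation, but none is an error rate. The criteria need only be met to some degree, and coherence is to be addressed partly through the same pathway model.
- **K is unknown.** Appendices Four and Five list well over 40 concepts, but many are indicators of a latent outcome, not predictors of it. Others are probably real influences: the note to Figure 2 gives coefficients of .58, .46, .43 and .36. The appendices therefore do not fix K.
- **Path lists and adjustment rules often sit in a statistical analysis plan.** Agreed, and their absence is not the point. The point is that the protocol's label and its described procedure disagree.

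**Conclusion.** The concern holds as a conflict between label and procedure in the protocol's own text. Sections 4.2 and 4.4 claim a confirmatory analysis; 4.4, 9.2.1 and 9.2.3 together describe a largely exploratory one, and 9.2.3 vouches for its robustness.

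The size is conditional. With 20 to 40 truly null candidates per model, independent tests and 5% per path, about 1 to 2 false paths per model are expected, with a 64–87% chance of at least one. One or more false paths per model is then likely, not certain, and the chance is lower if the test statistics are strongly correlated.

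A reader might go further and infer that several of the reported active ingredients are bound to be false, or multiply two by three outcome models and count six. The documents support neither. No number of null candidates is given, the gate may not open for all three outcomes, and some candidates are probably real. The word 'exploratory' in Section 4.5 should not be used as an admission either: it describes the initiative, not the analysis.

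**What to change.** Before follow-up data are analysed, for example in the Interim Report due in March 2013:

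1. For each of the child, parent and staff outcomes, name the specific mediator that represents each Figure 1 pathway: the circumstances of parents and children, project capacity, and service capacity. That is at most three paths per outcome, and fewer where a pathway is itself the outcome, as staff capacity may be.
2. Treat those paths as the confirmatory set, with Holm adjustment within each outcome. For three paths the ordered p-values are compared with 0.05/3 = 0.0167, 0.025 and 0.05. This holds the chance of any false path in the set at 5% per outcome, against 1 − 0.95³ = 14% unadjusted for three independent null paths. It does not adjust across the three outcomes or deal with confounding.
3. Report every other path, and every finding on who benefits, as exploratory.
4. Reword the aim in 4.4 so that it no longer seeks every significant source of variation, and limit the robustness claim in 9.2.3 to the paths named beforehand.
5. Keep the recalibration in 9.2.1 for before-and-after comparability.

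The cost is wording plus a short list of named paths. No new data are needed and no analysis is lost. The downside is that fewer pathways can be called confirmed.
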